Appendix A: Time & Events Schedule

| | Scrn (1-2) | Scn/ BL (1-2) | WK1 | WK2 | WK3 | WK4 | WK5 | WK6 | WK7 | WK8 | WK9 | WK10 | WK11 | WK12 | WK16 | Wk24 |
|--|---------------|---------------------|----------|-----|-----|-----|-----|-----|-----|-----|-----|------|------|------|------|------|
| ADOS-2 ¹ or CARS2 | X | | | | | | | | | | | | | | | |
| ADI-R | X | | | | | | | | | | | | | | | |
| WASI- II/WISC- V/KBIT | | X | | | | | | | | | | | | | | |
| DSM-V Checklist | X | | | | | | | | | | | | | | | |
| Inclusion/ Exclusion | X | X | | | | | | | | | | | | | | |
| Demographics | X | | | | | | | | | | | | | | | |
| Med/Psych Intake | X | | | | | | | | | | | | | | | |
| Family Med Hx (NIH Form) | X | | | | | | | | | | | | | | | |
| Randomization | | X | | | | | | | | | | | | | | |
| GUID Acquisition/ Record Form | X | | | | | | | | | | | | | | | |
| Con Meds | X | X | X | | X | | X | | X | | X | | X | X | X | X |
| Con Non Drug TX | X | X | X | | X | | X | | X | | X | | X | X | X | X |
| Vital Signs | | | biweekly | | | | | | | | | | | | X | X |
| | | X | X | | | | | | | | | | | | | |
| Height | X | X | | | | | | | | | | | X | | | X |
| Weight | X | X | | | | | | | | | | | X | | | X |
| Physical Exam (NIH Form) | X | X | | | | | | | | | | | | | | |
| Medical History (NIH Form) | X | | | | | | | | | | | | | | | |
| Tanner Staging | X | | | | | | | | | | | | | | | |
| Adverse Effects & Suicidality Ratings | X | X | X | | X | | X | | X | | X | | X | X | X | X |
| Blinded CGI S/I ¹ | | S | | | | | X | | | | | | | X | X | X |
| Unblinded CGI S/I | S | S | S/I | | S/I | | S/I | | S/I | | S/I | | S/I | S/I | S/I | S/I |
| Psychosocial Tx | X | X | | | | | | | | | | | | X | X | X |
| Laboratory | | | | | | | | | | | | | | | | |
| ECG | | X | | | | | | | | | | | | | | |
| Female Reproductive Status | | | X | | | | | | | | | | | | | |
| Urine Pregnancy | | | X | | | | | | | | | | X | | | |
| Safety labs | | | X | | | | | | | | | | | | | |

Confidential

Rush University Medical Center

| | | | | | | | | | | | | | | | | | |
|-----------------------------------|--|--|--|---|---|---|---|---|---|---|---|---|---|---|---|---|--|
| Social Skills Groups ¹ | | | | X | X | X | X | X | X | X | X | X | X | X | X | X | |
|-----------------------------------|--|--|--|---|---|---|---|---|---|---|---|---|---|---|---|---|--|

¹These assessments will be videotaped and/or administered electronically and recorded on a computer.

Confidential

Rush University Medical Center

| | Scrn (1-2) | Scn/ BL (1-2) | WK1 | WK2 | WK3 | WK4 | WK5 | WK6 | WK7 | WK8 | WK9 | WK10 | WK11 | WK12 | WK16 | Wk24 |
|--|---------------|---------------------|-----|-----|-----|-----|-----|-----|-----|-----|-----|------|------|------|------|------|
| Parent Questionnaires | | | | | | | | | | | | | | | | |
| ABC | X | | | | | | | X | | | | | | X | X | X |
| PDDBI-SV | | X | | | | | | X | | | | | | X | X | X |
| Griffith Empathy Scale | | X | | | | | | X | | | | | | X | X | X |
| Children's Communication Checklist | | X | | | | | | X | | | | | | X | X | X |
| CASI-5 | | X | | | | | | X | | | | | | X | X | X |
| Caregiver Strain | | X | | | | | | X | | | | | | X | X | X |
| Vineland 3 (Survey Form) | | X | | | | | | | | | | | | X | | X |
| SRS-2 | | X | | | | | | X | | | | | | X | X | X |
| RBS-R | | X | | | | | | X | | | | | | X | X | X |
| Autism Impact Measure | | X | | | | | | X | | | | | | X | X | X |
| Parent expectancy questionnaire | | X | | | | | | | | | | | | X | X | X |
| SSIS | | X | | | | | | | | | | | | X | X | X |
| Participant Assessments | | | | | | | | | | | | | | | | |
| Strange Stories Test | X | | | | | | | | | | | | | | | |
| Reading Mind in Eyes Test ¹ | | X | | | | | | | | | | | | X | X | X |
| DANVA2 ¹ | | X | | | | | | | | | | | | X | X | X |
| TAT ¹ | | X | | | | | | | | | | | | X | X | X |
| Biological motion task ¹ | | X | | | | | | | | | | | | X | X | X |
| AEDEA | | X | | | | | | | | | | | | X | X | X |
| Medication | | | | | | | | | | | | | | | | |
| Dosing Instructions | | | X | | X | | X | | X | | X | | X | | | |
| Medication Dispensing Log (staff) | | | X | | X | | X | | X | | X | | X | | | |
| Medication Compliance | | | X | | X | | X | | X | | X | | X | X | X | |
| Medication Diary Dispensed | | | X | X | X | X | X | X | X | X | X | X | X | | | |

Confidential

Rush University Medical Center

WORKS CITED

Official title: Integrated Oxytocin and Nonverbal, Emotion Recognition, and Theory of Mind

Training for Children With Autism Spectrum Disorder

NCT number: NCT02918864

Document date: 2/8/2021

Statistical Analysis Plan

Data Reduction and Outcome Variables. Safety and tolerability will be evaluated by comparing group differences on total counts and domains of the AE form and ratings on parent satisfaction surveys respectively. Efficacy analysis will follow analytic procedures used to derive social behavior impairment (SBI) and social cognition (SC) composites for the Seaver-NETT RCT16. First, principal components analysis (PCA) with promax rotation will be conducted on the primary social behavior impairment measures, the Nonverbal Communication and Social Relations subscales of the Children's Communication Checklist-2 (CCC-2) and the total score of the Griffith Empathy Scale (GEM). A separate PCA will be conducted on the primary social cognition outcomes, the Reading the Mind in the Eyes Test (RMET) and Diagnostic Analysis of Nonverbal Accuracy-2 (DANVA-2). The PCAs are used to confirm that these measures contribute to previously identified constructs in a field with no viable outcomes for higher-order core social impairments as well as to minimize floor and ceiling artifacts, effects of variability in response, and other sources of measurement error.

Prior to the PCAs, missing, invalid, and/or incomplete data will be removed. For SBI, observations missing one or more items on either CCC-2 subscale and/or greater than 30% of GEM items will be removed. For SC, observations with less than 50% of the responses (due to administrative error) on the RMET and/or DANVA2 will be removed. Provided these measures have high and near comparable component loadings on a single factor for each domain, thus confirming previous findings, they will be combined for separate composite scores for social behavior impairment (SBI) and social cognition (SC). To create the SBI composite score, total score on the GEM is reversed so that the higher scores reflect greater impairment as on the CCC-2. To create the SC composite score, percent correct was calculated for the RMET and DANVA-2 since they differ in total number of items and to adjust the denominator when all items were not presented due to administrative error. Subsequently, for each measure, scores will be standardized using the sample mean (and standard deviation) at baseline to account for change from baseline analyses, different and wide ranges of scores, and to ensure that composite scores across domains can be easily compared on the same scale (i.e., z-score). Following outlier detection (see below), standardized scores for each domain (SBI, SC) will then be averaged together to generate final composite scores at each time point. As such, a change in composite score reflects a change from baseline.

Outlier Detection. Individual scores from measures that are either influential points or outlier values (i.e., based on Cook's distance $> .5$ and/or Bonferroni-corrected outlier based on r-student residuals, respectively) and plausibly invalid (e.g., due to clinical reasons or administrative errors) will be removed. Composite scores will then be re-standardized and remaining extreme outliers (>3 SD above the mean for a specific timepoint) will be removed if they change the model significantly ($>10\%$ change in estimated values).

Data Analysis. Primary: Composite scores of both primary outcomes (i.e., SBI and SC) will be used as the response (i.e., outcome) variable in a series of mixed-effects linear regression models using the *lmer* package in *R Studio* to assess the effect of treatment condition (ION-ASD vs. Facilitated Play), time (e.g., change from baseline after 12 weeks), and condition X time interaction. Across all models, the individual participant will be included as the random effect. Age, verbal IQ, ADHD and generalized anxiety (from the Child & Adolescent Symptom Inventory-5 [CASI-5] T-scores) will be entered into the model to be examined as potential covariates and/or moderators to outcomes as in prior work. We will estimate effect sizes (standardized Betas) and confidence intervals (95%) acknowledging the likelihood that analyses may not permit definitive conclusions given the likely size of the confidence intervals. Finally, if the statistical assumptions of the model are not met (e.g., homoscedasticity, normality, linear relationships), generalized linear models with appropriate link functions or potential transformations of predictor variables will be assessed.

Secondary Outcomes. The linear mixed-effects models will also be used on secondary outcome measures: SRS T-score, mean Caregiver Strain Global rating scale. Responder (i.e., Clinical Global Inventory-Improvement [CGI-I]) analysis will be conducted using either a Chi-squared or Fisher's exact test (when observations are small such that $>20\%$ of cells have *expected* count <5) on the number of responders (i.e., CGI-I scores of 1-2) versus non-responders (i.e., CGI-I scores of 5-7) by group.

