4.1. Screening Assessments/Visits

Participants will complete the following assessments and procedures during the screening visit. Screening can be divided into two visits if necessary (estimated time=8-10 hours)

- Provide written informed consent/assent (subject and/or parent/caregiver/LAR). Consenting can take place virtually via a HIPAA compliant platform (i.e. Zoom) if needed to reduce the amount of in person interaction between study team and participant.
 - o Parent/guardian and participant will be required to be on the virtual call. Physical signature(s) will be obtained in person during first screening visit before any assessment administration can begin. A physical copy of the signed consent/assent will be given to participant at this time.
- *Demographics:* Information including age, race, ethnicity, family status and income will be collected.
- *Inclusion/Exclusion criteria checklist:* A checklist will be completed to ensure all inclusion and none of the exclusion criteria are met.
- *GUID acquisition form.* This form is designed to obtain all the information necessary in order to assign a GUID such as full name, date of birth, city of birth (as it is written on one's birth certificate).
- *Physical and mental health assessment:* participants suitable for the study undergo comprehensive medical evaluation by the Treating Clinician, including the following:
 - o *Family Medical History:* This form will ask for information about genetic, mental health and medical conditions of relatives of the subject.

- **Medical History:** This form will ask about the subject's medical history such as surgeries, medical procedures etc.
 - Females of childbearing potential will be asked to confirm the date of their last menstrual cycle and confirm contraception use if sexually active.
- **Adverse event ratings** systematic elicitation and screening of adverse events will be completed using a structured adverse events rating form. This will also be used at screening and baseline to obtain a comprehensive psychiatric and medical history of the patient; and assess suicidality.

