Participants entering the study will undergo the baseline assessments, which are anticipated to take approximately 6-10 hours to complete no more than 21 days from the last screening visit. The visit can be split into as many as three visits if this is better for the participant. The following measures will be completed: the CGI-S (Global and Social), AE rating form, the RMET, the CASI-5, the RBS-R, the SRS, the BASC-3, the PDDBI-SV, the Griffith Empathy Scale, the Children's Communication Checklist, the Caregiver Strain, the DANVA2, the TAT, and the Test, GEMEP emotion recognition test, and sensor-based social-communication monitoring tests..

Vineland Scales of Adaptive Functioning (3rd edition): The VABS-3 is a survey administered to a parent or caregiver is organized around four Behavior Domains: Communication, Daily Living Skills, Socialization, and Motor Skills. The VABS-3 will take the parent/caregiver/LAR approximately 20-60 (average 30) minutes to complete, depending on the subject's age and level of functioning.

Weekly Visits (1-11)

Interventions are delivered in 12-session modules occurring on a weekly basis. Groups will commence when all participants in a cycle have completed baseline evaluations and within 21 days of participant's last baseline visit. Participants will receive group treatment conditions as described in Section 5.1 (Treatment Conditions). Participants randomized to ION will also be prescribed 24 IU (3 puffs/nostril) of intranasal oxytocin 4 times/week to be administered by the parent 30-minutes prior to homework practice (3 x/week) and 30 minutes prior to each weekly group session.

Safety ratings during group: Weeks 1, 3, 5, 7, 9, 11 (or biweekly schedule depending on group start day/date)

Vital signs, temperature, and AE ratings will be completed in 6/12 sessions by a licensed physician on participants in all groups. In addition, the CGI-I (Global and Social) will be completed by the Study clinician. At

Confidential

Rush University Medical Center

Week 6, the CY-BOCS, the CASI-5, the RBS-R, the PDDBI-SV, the Griffith Empathy Scale, the Children's Communication Checklist, the Caregiver Strain and the ABC will be completed. In addition, a two week supply of study drug will be dispensed at weeks 1, 3, 5, 7, 9, 11. Unplanned visits will be permitted if there are any concerns about AEs. Safety visits are expected to take 15-20 minutes.

Week 6 (Midpoint)

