ICH E6 defines an AE as any untoward medical occurrence in a patient or clinical investigation subject administered a pharmaceutical product regardless of its causal relationship to the study treatment. An AE can therefore be any unfavorable and unintended sign (including an abnormal laboratory finding that is not directly obtained for purposes of the study), symptom, or disease temporally associated with the use of medicinal (investigational) product. The occurrence of an AE may come to the attention of study personnel during study visits and interviews of a study subject presenting for medical care, or upon review by a study monitor. All AEs including will be captured on the appropriate source documentation, the structured AE rating form. Information to be collected includes event description and clinician's assessment of severity.

8.2. Treatment Emergent Adverse Events (TEAEs).

Safety analysis will focus on TEAEs. Medical and behavioral conditions will be evaluated at screening and baseline, and will only be considered TEAEs if the severity increases significantly after a participant has completed a treatment session. All TEAEs will be documented during the course of the study regardless of relationship to treatment. All TEAEs will be followed to adequate resolution. If a TEAE is also a serious adverse event (SAE) and/or Unexpected Problem (UP), the SAE or UP forms will also be completed. If a TEAE is both a SAE and UP, only the SAE form and the AE FORM will be completed.

8.3. *Suicidality Assessment.*

Suicidality assessments will be completed for each participant during visits with Study clinicians. The clinician will determine if the participant understands the concept of death and making one's self die or hurt. If the participant is able to understand these concepts, they will be asked if they have any thoughts about wanting to die, wanting to hurt themselves, wanting to kill themselves, and if s/he has done anything to hurt himself/herself so s/he would die or have done anything to hurt himself/herself for any other reason. If the participant is deemed not to understand these concepts, his/her caregiver will be asked the above questions. The caregiver will also be asked to rate if this is a significant changes in severity or frequency from the participant's behavior at baseline.

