- Mild*: events require minimal or no treatment and do not interfere with the subject's daily activities.
- Moderate*: events result in a low level of inconvenience or concern with the therapeutic measures. Moderate events may cause some interference with functioning.
- Severe*: events interrupt a subject's usual daily activity and may require systemic drug therapy or other treatment. Severe events are usually incapacitating.
- Life-threatening*: Substantial risk dying or requires intervention to prevent death.
- Death related to AE*: Subject died as a result of the event, self-explanatory.

Changes in the severity of an AE will be documented to allow an assessment of the duration of the event at each level of intensity to be performed. Adverse events characterized as intermittent require documentation of onset and duration of each episode.

Relationship to Study Treatment. Study clinicians will assess and document whether the AE is related to treatment condition. However, the relationship to study treatment will not be a factor in determining whether or not an AE is reported in this study. If there is any doubt as to whether a clinical observation is an AE, the event will be reported. All AEs must have their relationship to study product assessed using the terms: associated or not associated. In a clinical trial, the study product must always be suspect. To help assess, the following guidelines are used.

- Certain*: The adverse event and administration of the study drug are related in time, and a direct association can be demonstrated.
- Probably*: The adverse event and administration of the study drug are reasonably related in time, and the adverse event is more likely explained by the study drug than other causes.
- Possible*: The adverse event and administration of the study drug are reasonably related in time, and the adverse event can be explained equally well by causes other than the study drug.

Confidential

Rush University Medical Center

- *Unrelated*: The adverse event is clearly explained by another cause not related to the study drug.
- *Unknown or not applicable*

Reporting Procedures: Serious Adverse Events & Unanticipated Problems

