8.8. Statistical analysis

Specific Aim 1 & Exploratory Aim 1: Safety and tolerability will be analyzed by analyzing for group differences on total scores and domains of the AE form and satisfaction surveys respectively. Efficacy analysis will be follow analytic procedures used to derive social behavior and social cognition composites for the Seaver-NETT RCT¹⁶. First, a principal components analysis with varimax (orthogonal) rotation will be conducted on subscales of the primary social behavior measures - Griffith Empathy Scale and CCC-2; and raw total scores on primary social cognition outcomes – RMET and DANVA2. The PCA is used to develop composite scores in a field with no viable outcomes for higher-order core social impairments as well as to minimize floor and ceiling artifacts, effects of variability in response, and other sources of measurement error. Variables with high factor loadings for subscales will be entered into composite score development for the social cognition and social behavior composites. Missing, invalid, and/or incomplete data (i.e. more than 30% items missing when not pre-defined by scale) will be excluded from the factor analysis.

A linear mixed model analysis will be conducted on all participants with at least two of four available time points (Wk 0, Wk 12, 1-mon, 3-mo). Composite scores of co-primary outcomes social behavior and social cognition will be used as the response variable; treatment condition, time, and condition * time interactions will be covariates. Verbal IQ will also be entered into the model in exploratory moderator analyses. We will estimate effect sizes (Cohen's d) and confidence intervals (95%) acknowledging the likelihood that analyses may not permit definitive conclusions given the likely size of the confidence intervals.

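### The safety outcome is defined in three inconsistent ways, and the SAP's version, total counts on the AE form, carries neither the protocol's TEAE restriction nor any allowance for follow-up

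*SAP*

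**What the plan says.** Protocol 2.1 makes safety and tolerability part (A) of the primary aim. Three places then say how safety will be analysed.

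- Protocol 8.2: "Safety analysis will focus on TEAEs". Conditions noted at screening and baseline "will only be considered TEAEs if the severity increases significantly after a participant has completed a treatment session".
- Protocol 8.8: the analysis is of "group differences on total scores and domains of the AE form".
- SAP, Data Reduction and Outcome Variables: safety is evaluated by "comparing group differences on total counts and domains of the AE form".

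The AE form is not only an on-treatment instrument. Protocol 4.1 says of it: "This will also be used at screening and baseline to obtain a comprehensive psychiatric and medical history of the patient". Appendix A schedules it at screening and baseline, then at Weeks 1, 3, 5, 7, 9, 11, 12, 16 and 24. Protocol 5.2 applies the same schedule to both arms: "AE ratings will be completed in 6/12 sessions by a licensed physician on participants in all groups". Protocol 8.5 adds: "Adverse events characterized as intermittent require documentation of onset and duration of each episode".

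Neither document gives a per-child proportion, a rule for counting a persisting event once, an AE window for the analysis, or an adjustment for length of follow-up. No test or interval is tied to the safety comparison.

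**The concern.** Scores, counts and treatment-emergent events are different quantities, and a single data set can give a different answer on each. The SAP is the document an analyst will program from, and it names the version with the fewest restrictions. As worded, it leaves open whether screening and baseline entries are summed, whether a complaint present at several visits counts once or several times, and whether the off-drug visits at Weeks 16 and 24 belong in the total.

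A raw total also rises with the number of forms completed. A child who leaves early contributes fewer forms, so the total mixes how often events occur with how long the child was observed. It also does not give the share of children who had an event, which is what a reader of a pilot safety result first wants to know.

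**Working it through.** The documents give no event rate, event count or precision figure for safety, so there is no stated safety figure to reproduce. The check has a textual part and an illustration on assumed values.

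**1. The three definitions applied to one child (hypothetical).** A complaint present at baseline and unchanged in severity at Weeks 3, 5 and 7 gives no TEAE under protocol 8.2. It gives up to four entries if every form is summed (baseline plus three), or three if only post-start forms are. Under 8.8 it gives a score whose scale the protocol does not state. A new complaint at Week 3 that persists to Week 7 is one event but up to three form entries.

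**2. Inputs.** From the documents: two pre-treatment forms; nine forms from Week 1 (seven up to Week 12, two after treatment); 1:1 allocation (3.5); 5% attrition with no split by arm (8.9). Assumed: 0.50 events per form in controls and 0.65 on ION-ASD, so a true rate ratio of 1.30; full control follow-up; a share w of the ION-ASD arm leaving after k = 2 or 3 forms.

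**3. Pre-treatment entries, if they were summed.** Expected totals without stopping are 0.65 × 9 = 5.85 and 0.50 × 9 = 4.50, a difference of 1.35. Adding two forms at 0.50 to both arms gives 6.85 and 5.50. The difference is still 1.35, but the ratio falls from 1.30 to 6.85/5.50 = 1.25. So a difference is not biased and a ratio shrinks. The added entries also cost precision. In a Poisson simulation (assumed 3 treatment-emergent events per control child, rate ratio 1.5, 35 per arm, t-test on counts), adding 3 pre-treatment items per child lowers power from about 0.89 to 0.67.

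**4. Early stopping in the ION-ASD arm only.** Ratio of totals = 0.65 × [(1 − w) × 9 + w × k] / (0.50 × 9).

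| w | k | ION-ASD total | Ratio to 4.50 |
|---|---|---|---|
| 5% | 2 | 0.65 × 8.65 = 5.62 | 1.25 |
| 5% | 3 | 0.65 × 8.70 = 5.66 | 1.26 |
| 20% | 2 | 0.65 × 7.60 = 4.94 | 1.10 |
| 20% | 3 | 0.65 × 7.80 = 5.07 | 1.13 |

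Dividing events by forms completed returns 0.65/0.50 = 1.30 in every row. To bring the ratio of totals down to 1, the arm would have to lose 1 − 1/1.30 = 23% of its follow-up.

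**5. Direction.** With the same w and k in both arms, the bracket cancels and the ratio stays 1.30. With 5% stopping in controls only and k = 2, it is 5.85/(0.50 × 8.65) = 1.35, so the bias reverses.

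**6. Pooling the off-drug visits.** If the ratio of 1.30 held only for the seven forms up to Week 12 and was 1 afterwards (assumed), then with no stopping the pooled ratio would be (0.65 × 7 + 0.50 × 2)/4.50 = 5.55/4.50 = 1.23. This is a separate reason to show the two windows apart. It also means that step 4, which applies 1.30 to all nine forms, somewhat overstates the signal lost through stopping.

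**The case against.** A reader might infer that the SAP counts pre-treatment conditions as safety events. The documents do not say so. The SAP is silent on which visits are summed, and protocol 8.2 would exclude those entries; read together, the two documents can be reconciled. Even if the entries were summed, randomization balances them in expectation, and both documents speak of group differences, which such entries do not bias.

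A reader might also infer that early stopping makes oxytocin look safer. That needs more stopping on ION-ASD than in control, and AE rating that is lost afterwards. The documents establish neither. The 5% attrition has no split by arm. Protocol 5.2 asks children who withdraw to complete the endpoint procedures, which include the AE form, at their final visit. Protocol 8.2 has TEAEs followed until they resolve, and the event that led to stopping would itself be counted. Nor do the documents state a rule by which a non-significant comparison would be declared safe, and a DSMB monitors adverse events and drop-outs separately.

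Finally, protocol 8.5 calls for onset and duration of each intermittent episode and for changes in severity, so the data would allow a continuing event to be counted once.

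These points limit the direction and size of any bias. They do not supply the missing definition. Protocol 8.8 and the SAP still name different quantities, and neither is the quantity in 8.2. On follow-up, protocol 3.7 speaks of withdrawal from study treatment, while 4.2, 4.3 and the stopping procedures in 8.5 also provide for leaving the study. Continued biweekly AE rating after an early stop is not stated anywhere. Records that permit once-only counting are not a rule that requires it.

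**Conclusion.** The concern holds as a problem of definition. An outcome in the primary aim is specified in three inconsistent ways, and the SAP's version omits the protocol's own restriction, depends on the number of forms completed, can count a continuing complaint repeatedly, and does not yield the share of children affected. It should be corrected before analysis.

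The documents do not support saying that pre-treatment conditions are counted, or that the drug will look safer. The first is an ambiguity that protocol 8.2 would resolve if carried into the SAP. The second is conditional. At the planned 5% attrition the shift is small even if all of it falls on ION-ASD (1.30 to about 1.25). The larger shift, to 1.10–1.13, needs an assumed 20% stopping in that arm alone with later forms lost. The event rates, the rate ratio and the timing of stopping are all assumptions.

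**What to change.** In the SAP:

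1. Replace total counts with TEAEs as defined in protocol 8.2, and reconcile the total scores in protocol 8.8 with that definition.
2. Report the number and percent of children with at least one TEAE by arm, overall and by AE-form domain, as a risk difference with 95% CI.
3. Count each continuing event once per child.
4. Add a supportive event rate per unit of follow-up: a count model with log exposure as offset, or simple exposure-adjusted rates if events are few.
5. Show the on-treatment window and the post-treatment window (Weeks 16 and 24) separately, and state which AE forms are expected after an early stop.

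The cost is SAP wording, an aligning edit to protocol 8.8 and slightly more analysis; the AE data are already planned. Intervals will be wide. If about half the children in each arm had a TEAE (assumed), the half-width would be 1.96 × √(2 × 0.25/35) = 0.23 with 35 per arm (Phase 2 in protocol 3.1) and 1.96 × √(2 × 0.25/25) = 0.28 with 25 per arm (protocol 8.9). That imprecision belongs in the report, in keeping with the caution both documents already express about their confidence intervals.
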